6.2 Toxicity Management

The toxicity management of the AEs including safety topics of interest, consists of safety monitoring (review of AEs on an ongoing basis), and, if applicable, interruption of study drug dosing with appropriate clinical management and/or discontinuation of the subjects from study drug. The management of specific AEs and laboratory parameters is described below.

For subjects who discontinue study drug but continue study participation and are on standard of care therapies, these toxicity management requirements do not apply (including alerts from the central lab) and any intolerance to standard of care therapies should be managed by the prescribing physician.

Serious Infections: Subjects should be closely monitored for the development of signs and symptoms of infection during and after treatment with study drug. Study drug should be interrupted if a subject develops a serious infection or a serious opportunistic infection. A subject who develops a new serious infection during treatment with study drug should undergo prompt diagnostic testing appropriate for an immunocompromised subject. As appropriate, antimicrobial therapy should be initiated, and the subject should be closely monitored. Study drug may be restarted once the infection has been successfully treated or resolved. Subjects who develop active TB or experience Hepatitis B reactivation must be discontinued from study drug.

Malignancy: Subjects who develop malignancy other than nonmelanoma skin cancer (NMSC) or carcinoma in situ of the cervix must be discontinued from study drug. Information including histopathological results should be queried for the confirmation of the diagnosis.

Psychiatric Symptoms: Subjects who develop new onset suicidal ideations or attempt should be discontinued from study drug. For subjects who develop other clinically significant psychiatric symptoms considered related to study drug by the investigator (for example, abnormal/vivid dreams and nightmares), study drug interruption or discontinuation should be considered if the symptoms are severe (CTCAE psychiatric disorders Grade 3 or higher), persistent or worsening.

Neurologic Symptoms: Subjects with new onset related seizure(s) should be discontinued from study drug and should undergo appropriate prompt diagnostic evaluation and intervention. For subjects who develop clinically significant new onset tremor or other neurological condition considered related to study drug by the investigator, study drug interruption or discontinuation should be considered if the symptoms are severe (CTCAE Grade 3 or higher), persistent or worsening.

Surgery: Subjects who undergo emergency surgery should have study drug interrupted at the time of the surgery. After emergency surgery, reintroduction of study drug is allowed once the physician has examined the surgical site and determined that it has healed and there is no sign of infection.

Laboratory parameter toxicity guidelines are presented in [Table 2](#).

Table 2. Laboratory Parameter Toxicity Guidelines

Laboratory Parameters Toxicity Guidelines		
Absolute neutrophil count (ANC)	< 1000 cells/ μ L	Interrupt study drug dosing and redraw lab with a new sample. 
• If value is confirmed, continue to withhold study drug until value returns to normal reference range or baseline value.
	< 500 cells/ μ L	Interrupt study drug dosing and redraw lab with a new sample. 
• If value is confirmed, discontinue study drug.
Absolute lymphocyte counts (ALC)	< 500 cells/ μ L	Interrupt study drug dosing and redraw lab with a new sample. 
• If value is confirmed, continue to withhold study drug until value returns to normal reference range or baseline value.
Platelet count	< 50,000 cells/ μ L	Interrupt study drug dosing and redraw lab with a new sample. 
• If value is confirmed, continue to withhold study drug until value returns to normal reference range or baseline value.
ALT or AST	ALT or AST > 8 \times ULN	Interrupt study drug dosing immediately and redraw lab with a new sample. 
• If value is confirmed, discontinue study drug and complete supplemental hepatic eCRF.
	ALT or AST > 5 \times ULN	Interrupt study drug dosing immediately and redraw lab with a new sample. 
• If value is confirmed for > 2 weeks of duration, discontinue study drug and complete supplemental hepatic eCRF.
	ALT or AST > 3 \times ULN along with appearance of fatigue, nausea, vomiting, right upper quadrant pain or tenderness, fever, rash, and/or eosinophilia (> 5%).	Interrupt study drug immediately and redraw lab with a new sample. If confirmed ALT or AST > 3 \times ULN by repeat testing with new sample along with appearance of fatigue, nausea, vomiting, right upper quadrant pain or tenderness, fever, rash, and/or eosinophilia (> 5%) discontinue study drug and complete supplemental hepatic eCRF.
	ALT or AST > 3 \times ULN and either a total bilirubin > 2 \times ULN or an international normalized ratio (INR) > 1.5	Interrupt study drug immediately and redraw lab with a new sample. If ALT or AST > 3 \times ULN is confirmed and total bilirubin > 2 \times ULN or international normalized ratio (INR) > 1.5, discontinue study drug and complete supplemental hepatic eCRF.
	Subjects who are HBC Ab+ and HBV DNA negative at Screening who develop: ALT or AST > 5 \times ULN OR ALT or AST > 3 \times ULN, if an alternative cause is not readily identified	Interrupt study drug immediately and redraw lab with a new sample. 
• If value is confirmed, send HBV DNA by PCR.• If HBV DNA by PCR is positive, discontinue study drug and complete supplemental hepatic eCRF.

7 STATISTICAL METHODS & DETERMINATION OF SAMPLE SIZE

7.1 Statistical and Analytical Plans

Complete and specific details of the statistical analysis will be described and fully documented in the Statistical Analysis Plan (SAP).

The Primary Analysis will be conducted after all subjects have either completed the Week 8 assessment or withdrawn from the study. The final analysis will be conducted after all subjects have either withdrawn from the study or completed the Week 16 assessment and the safety Follow-up Visit.

7.2 Definition for Analysis Populations

The ITT Population consists of all subjects who received at least 1 dose of study drug. The ITT Population will be used for all efficacy and baseline analyses.

The Safety Population consists of all subjects who received at least 1 dose of study drug. The Safety Population will be used for all safety analyses.

7.3 Handling Potential Intercurrent Events for the Primary and Secondary Endpoints

For both the primary and secondary endpoints, data collected will be used regardless of premature discontinuation of study drug. Subjects will be considered as non-responders after the start of rescue medication (initiation or dose escalation of UC-related corticosteroids).

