- ✓ 9. No known active SARS-CoV-2 infection. If a subject has signs/symptoms suggestive of SARS-CoV-2 infection, the subject must have a negative molecular (e.g., PCR) test or 2 negative antigen test results at least 24 hours apart. Note: SARS CoV-2 diagnostic tests should be applied following local requirements/recommendations.
 - Subjects who do not meet SARS-CoV-2 infection eligibility criteria may only resume screening for the study after they meet the following SARS-CoV-2 infection viral clearance criteria:
 - At least 10 days since the first positive test result has passed in asymptomatic patients or at least 10 days since recovery, defined as resolution of fever without use of antipyretics and improvement in symptoms.
- ✓ 10. No current diagnosis of CD or inflammatory bowel disease-unclassified (IBD-U).
- ✓ 11. No extent of inflammatory disease limited to the rectum as assessed by screening endoscopy.
- ✓ 12. No currently known complications of UC such as:
 - fulminant colitis,
 - toxic megacolon,

- previous colectomy (total or subtotal), or
- any other manifestation that might require surgery while enrolled in the study.

✓ 13. Subject must not have current suicidal ideation with plan within the prior month, via answering "yes" to questions 4 or 5 to the suicidal ideation portion of the Columbia-Suicide Severity Rating Scale (C-SSRS) completed at Screening and Baseline, or any history of suicide attempt(s) within the last 2 years.

✓ 14. No history of seizures (excluding history of a single childhood febrile seizure before age 5), epilepsy, convulsions, significant head injury, or other significant neurologic conditions.

✓ 15. Subjects must not have an ostomy or ileoanal pouch.

✓ 16. No history of radiation colitis or ischemic colitis.

✓ 17. No history of any malignancy except for successfully treated non metastatic cutaneous squamous cell or basal cell carcinoma or localized carcinoma in situ of the cervix.

✓ 18. No history of clinically significant (per investigator's judgment) drug or alcohol abuse within the last 12 months.

✓ 19. No history of clinically significant medical conditions or any other reason that the investigator determines would interfere with the subject's participation in this study or would make the subject an unsuitable candidate to receive study drug.

✓ 20. No history of an allergic reaction or significant sensitivity to constituents of the study drug (and its excipients) and/or other products in the same class.

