8.0 Handling of Potential Intercurrent Events for the Primary and Secondary Endpoints

The primary and secondary efficacy endpoints (defined in Section 3.1 and Section 3.2) will be analyzed based on the ITT Population and the following methods will be used to address potential intercurrent events.

Intercurrent events (ICE):

ICE1: Premature discontinuation of study treatment

A treatment policy strategy will be used to handle ICE1, namely, available data collected will be used regardless of premature discontinuation of study treatment.

ICE2: Initiation or dose escalation of UC-related corticosteroid (defined as below) or initiation of any TIM therapy (including biologics and non-biologics) for UC. A composite strategy will be used to handle ICE2, namely, subjects will be considered as not achieving response at or after ICE2.

UC-related corticosteroid ICE is defined as:

- Subjects who were not on UC-related corticosteroids (systemic or locally acting corticosteroids for UC) at Baseline initiate UC-related corticosteroids during the study.
- Subjects who were on UC-related systemic corticosteroids at Baseline who have dosage increased to greater than the prednisone equivalent dose of corticosteroid taken at Baseline, or initiation of any rectal corticosteroids during the study regardless of rectal corticosteroid dose.

The time of ICE2 is defined as the date when either of the two scenarios above first occurs for a subject. As such, the subject will be considered as a "non-responder" for the efficacy endpoint on or after the date of ICE2 through the end of the study. In the scenario when both ICE1 and ICE2 occur, data will be used on or after the date of ICE1 until ICE2, which the subject will be considered as a "non-responder" for the efficacy endpoint on or after the date of ICE2.

Same intercurrent events handling approaches will be used for additional efficacy endpoints, except for:

- For continuous endpoints, data collected on or after ICE2 will be excluded from the analysis (i.e., treated as missing data) handled by mixed effect model repeat measurement (MMRM).
- For time-to-event endpoint, subjects will be censored at ICE2.

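### UC-related surgery is not named as an intercurrent event, so a subject operated on during the study can be counted as a responder on the diary-only endpoints

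*Protocol*

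**What the plan says.** Protocol Section 7.3 sets two rules for the primary and secondary endpoints. For subjects who stop treatment, "data collected will be used regardless of premature discontinuation of study drug". For rescue, "Subjects will be considered as non-responders after the start of rescue medication (initiation or dose escalation of UC-related corticosteroids".

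SAP Section 8.0 has the same structure. ICE1 is handled by treatment policy: "available data collected will be used regardless of premature discontinuation of study treatment". The composite event is wider than in the protocol: "ICE2: Initiation or dose escalation of UC-related corticosteroid (defined as below) or initiation of any TIM therapy (including biologics and non-biologics) for UC". SAP Tables 1 and 2 repeat these two events.

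Surgery appears elsewhere, but never as an analysis rule:
- **Entry (Protocol 5.1).** Previous colectomy is excluded, as is any manifestation that might need surgery during the study. Also: "Subjects must not have an ostomy or ileoanal pouch".
- **Toxicity management (Protocol 6.2).** "Subjects who undergo emergency surgery should have study drug interrupted at the time of the surgery". Further: "After emergency surgery, reintroduction of study drug is allowed once the physician has examined the surgical site and determined that it has healed", if there is no sign of infection.
- **Withdrawal (Protocol 5.5).** Colectomy is not among the listed reasons, but the list is expressly open-ended.
- **Follow-up (Protocol 5.6).** Subjects who stop study drug stay on the visit schedule unless they withdraw consent.

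Under SAP Section 9.2.1, non-responder imputation (NRI) applies when the evaluation in the visit window is missing.

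**The concern.** A subject whose UC leads to removal of the colon, or to an ostomy or pouch, has failed treatment on any ordinary reading. The protocol keeps such anatomy out at entry, but the analysis has no matching rule for a subject who acquires it on study. If the subject has had no corticosteroid or TIM start, the composite rule does not apply. If the diary is completed, NRI does not apply either.

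Clinical response per Partial Adapted Mayo is a secondary endpoint built only from the diary SFS and RBS, so it can be scored without an endoscopy. The additional endpoints RBS = 0, SFS of 1 or less, time to response, and change in SFS and RBS also come from the diary. For the binary response endpoints, an error of this kind can only turn a failure into a success. In a single-arm study against historical placebo, no concurrent arm offsets it. Without a rule set in advance, the classification would be settled in an open-label study with the outcome known.

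**Working it through.** **Inputs**
- Partial Adapted Mayo = SFS + RBS, each scored 0 to 3 (Operations Manual 8.2).
- Response: a fall of at least 1 point and at least 30%, plus an RBS fall of at least 1 or RBS of 1 or less (Protocol 3.1, SAP 3.0).
- Entry: Adapted Mayo 5 to 9 with endoscopic subscore (ESS) 2 or 3 (Protocol 5.1).
- N = 40 (Protocol 7.8). Treatment prior Beta(0.5, 0.5) (SAP 9.3.2). Placebo prior for this endpoint Beta(20.9, 38.4) (SAP Table D-1).
- Assumption: no rectal blood is recorded after surgery, so RBS = 0. The documents do not say how the diary is scored after an ostomy or pouch.
- Simplification: integer subscores, although the plan averages over 7 days.

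**The plan's own figures.** Table D-1 gives a placebo rate of 35%. The prior mean is 20.9/(20.9 + 38.4) = 0.352, and the pooled rate is (64 + 51)/(154 + 174) = 115/328 = 0.351, so the figure reproduces. The sample-size statement (more than 90% probability) concerns the primary endpoint, whose placebo rate and prior are redacted. With assumed placebo rates of 3% to 25% and prior effective sizes of 30 to 400, the probability is at least 0.980. That statement holds and is not touched by this point.

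**Step 1: can such a subject be a responder?** Baseline SFS 3 + RBS 2 = 5. After surgery, with SFS at its worst value, 3 + 0 = 3. The fall is 2 points and 2/5 = 40%, with RBS 0. All conditions are met.

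**Step 2: how general is this?** Entry requires SFS + RBS + ESS of at least 5 with ESS at most 3, so SFS + RBS is at least 2. Of the 16 integer pairs, (0,0), (0,1) and (1,0) drop out, leaving 13. With Baseline sum s and post-surgery score k (RBS = 0), the 30% condition is (s - k)/s >= 0.30, or s >= k/0.7.

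| Post-surgery SFS | Baseline sum needed | Eligible pairs that become responders |
|---|---|---|
| 3 | 5 or more (3/0.7 = 4.3) | 3 of 13: (2,3), (3,2), (3,3) |
| 2 | 3 or more (2/0.7 = 2.9) | 10 of 13: all but (0,2), (1,1), (2,0) |
| 0 or 1 | 2 or more | 13 of 13 |

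Baseline (3,1) with SFS still 3 falls from 4 to 3, which is 25%, and is not a response. Responder status is possible, not automatic.

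**Step 3: size.** One subject is 1/40 = 2.5 points on the observed rate. The documents give no surgery rate. If 0, 1 or 2 of 40 were affected (an assumption), the rate would be too high by 0, 2.5 or 5 points.

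For r responders, the posterior mean difference is (0.5 + r)/41 - 0.352. The posterior probability is that of Beta(0.5 + r, 40.5 - r) exceeding Beta(20.9, 38.4), by numerical integration.

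| Responders of 40 | Posterior mean difference | P(difference > 0) |
|---|---|---|
| 20 | 0.148 | 0.931 |
| 19 | 0.123 | 0.893 |
| 18 | 0.099 | 0.841 |

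Recoding one subject lowers the mean difference by 1/41 = 2.4 points. At 20 of 40 it also takes the probability below 0.90, the level used to size the primary endpoint. This is illustrative only, because no threshold is set for secondary endpoints.

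**The case against.** The strongest reply is that the gap is narrow and mostly covered already.

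- Entry excludes fulminant colitis, toxic megacolon and manifestations likely to need surgery. A subject who starts or escalates corticosteroids, or starts TIM therapy under the SAP, is a non-responder from that date. A subject with too few diary days is a non-responder by NRI. All of this stands and makes the event uncommon.
- A reader might infer that the plan expressly keeps all post-surgery data. It does not: both data-retention rules are limited to stopping study drug. Use of post-surgery diaries follows from those rules and the absence of any surgery rule.
- A reader might take surgery for colon cancer or high-grade dysplasia as a typical route. Protocol 5.5 and Operations Manual 3.16 lead to discontinuation from the study, so later diaries would ordinarily not exist. Perforation, named in Protocol 2.1 among the most severe manifestations, is the better example.
- A reader might count surgery up to Week 16. The exposed secondary endpoint is at Week 8, so later surgery can affect only the additional endpoints.
- The existing ICE2 handling censors time to response and drops continuous values. It would not count surgery as failure on those endpoints. This is correct and limits what the fix achieves.

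What remains is that no rule in either document makes a subject with completed post-surgery diaries and no drug rescue a non-responder.

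**Conclusion.** The point holds as a cheap improvement. Among the primary and secondary endpoints, it concerns clinical response per Partial Adapted Mayo at Week 8; beyond these, it concerns the additional diary endpoints. It rests on four conditions: UC-related surgery on study, no prior corticosteroid or TIM start, continued follow-up, and a completed diary with no rectal blood recorded. The size is 2.5 points per subject at N = 40, for an event assumed rare because the documents give no rate.

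A reader might infer that any subject with a colectomy becomes a responder, or that the primary result is at risk. The documents support neither. With post-surgery SFS at 3, only 3 of 13 eligible Baseline pairs meet the definition. Endoscopic improvement, endoscopic remission and the Adapted Mayo endpoints need an ESS, and without one NRI gives non-response. That protection is large but not complete, since the ESS is the worst of the observed segments and a remaining segment might still be scored. In the as-observed analysis, such a subject would be dropped rather than counted as a failure.

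**What to change.** Add UC-related surgery (colectomy, ostomy or ileoanal pouch) to the composite event in Protocol Section 7.3, SAP Section 8.0 and SAP Tables 1 and 2. This is an analysis rule and changes no patient care.

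- **Binary endpoints:** non-responder from the surgery date to the end of the study.
- **Time to clinical response:** do not let a response be first declared from post-surgery diaries. Censoring at surgery, as for ICE2 now, achieves this but does not count surgery as failure; the SAP should say so.
- **Change in SFS and RBS:** exclude post-surgery values as under existing ICE2 handling. This removes the spurious values but likewise does not count surgery as failure.

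The protocol's rescue definition omits TIM therapy while the SAP includes it, so the edit is needed in both documents.

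The cost is one phrase in each place plus a source for the surgery date, which must be taken from the adverse event or serious adverse event records. Hospital admission makes an event serious under Protocol 6.1, but the procedure form named there is listed with cardiovascular procedures, so the team should confirm that the operation date itself is recorded. The reported response rate may be slightly lower.

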7.4 Statistical Analyses for Efficacy

Summary and Analysis of the Primary Endpoint

The Primary Analysis will be performed after all subjects have either completed the Week 8 assessment or withdrawn from the study. The final analysis will be conducted after all subjects have either withdrawn from the study or completed the Week 16 assessment and the safety Follow-up Visit.

The primary efficacy endpoint is achievement of endoscopic improvement at Week 8.

Analysis of the primary efficacy endpoint will be conducted on the ITT Population. Comparison of the primary efficacy endpoint will be performed between the ABBV-668 treatment group and historical placebo group using the Bayesian approach with prior distribution obtained from meta-analysis for the historical placebo data, and non-informative prior for the ABBV-668 treatment group. The placebo prior will be determined based on placebo data from similar trials available before the Primary Analysis database lock. The posterior probability of rate difference > 0 given data will be calculated. The mean difference and the corresponding 95% credible interval will be provided.

For the analyses of the primary and secondary endpoints, the primary approach for handling missing data will be Non-Responder Imputation incorporating multiple imputation (NRI-MI). Subjects with missing data will be counted as non-responders, except when missing at random can be reasonably assumed, which will be handled by multiple imputation. For example, missing due to COVID-19 logistical restriction or due to political conflict will be handled by multiple imputation.

Summary and Analysis of Secondary Endpoints

Similar analysis described above comparing ABBV-668 treatment group and historical placebo group will be performed for the secondary endpoints.

7.5 Statistical Analyses for Safety

Safety analyses will be performed using the Safety Population, as defined in Section 7.2. Safety will be assessed by AEs, physical examination (including neurological exams), C-SSRS evaluation, laboratory assessments, and vital signs. Missing safety data will not be imputed. Details for each safety endpoint analysis will be provided in the SAP.

Treatment-emergent adverse events (TEAEs) will be tabulated by Medical Dictionary for Regulatory Activities (MedDRA) system organ class (SOC) and by preferred term (PT) for the treatment group. Summaries of SAEs, deaths, AEs leading to discontinuation and AESIs will be provided as well. For selected laboratory and vital signs parameters, mean change from Baseline and percentage of subjects with evaluations meeting the criteria for pre-defined potentially clinically significant (PCS) values will be summarized.

7.6 Interim Analysis

Interim analyses may be performed to provide information for future study decisions.

